11.4. Safety Evaluation

The primary assessment of safety will be based on the frequency of treatment-emergent adverse events (TEAEs), serious adverse events (SAEs) and on the frequency of clinically notable abnormal vital signs, electrocardiograms (ECGs) and laboratory values. Other safety evaluations include changes in vital signs, changes in clinical laboratory evaluations, and changes in ECGs, extra pyramidal symptoms (EPS) using the Barnes Akathisia Scale, Simpson-Angus Scale and the AIMS, physical exam findings during treatment, and suicide ideation (C-SSRS) and behavior events.

11.4.1.1. Adverse Events

Adverse events will be recorded throughout the study and at early discontinuation. Adverse events and medical conditions will be coded using the Medical Dictionary for Regulatory Activities (MedDRA) coding dictionary. Treatment-emergent adverse events will be defined as those events, which are newly occurring or worsening from baseline. In all cases only treatment emergent adverse events will be summarized.

Treatment-emergent adverse events will be summarized within each treatment group by primary system organ class and preferred term. (NOTE: In any given category [e.g. body system] a patient will only be counted once.) The incidence rates of TEAEs will be analyzed as described in the SAP. Similar displays will be provided for SAE and prior (conditions ending prior to the first dose of study medication) and current (conditions present while on study medication) medical conditions.

Adverse events will further be categorized by severity, relationship to study medication, and action taken. Other information collected will be listed, as appropriate. Any event starting more than 3 days after the final dose of study medication will be excluded from the above tables and only listed, unless the event caused discontinuation.

The proportions of patients experiencing SAEs and AEs resulting in discontinuation from the study will be summarized by treatment groups.

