Subjects who complete the Double-Blind Treatment Period will be eligible to participate in the optional OLE Phase. Eligible subjects will enter the 7-day OLE Titration Period where iloperidone will be titrated to 24 mg/day total daily dose given as a bid regimen (12 mg bid). The target dose for CYP2D6 poor metabolizers is 12mg/d (6 mg bid). Subjects will then enter the OLE Maintenance Period in which subjects will be treated with iloperidone for up to 52 weeks.

Criteria for evaluation:

Mean baseline-to-endpoint change in total score using following parameters:

Efficacy:

- Young Mania Rating Scale (YMRS)
- Overall and mania severity of illness for Clinical Global Impression of Severity (CGI-S)
- Clinical Global Impression of Change (CGI-C)
- Montgomery-Asberg Depression Rating Scale (MADRS)

Safety:

- Adverse Events (AEs) and proportion of patients withdrawing due to AEs
- EPS scale scores as measured by Simpson-Angus Scale (SAS), Abnormal Involuntary Movement Scale (AIMS), and Barnes Akathisia Rating Scale (BARS)
- Metabolic risk factors, clinical chemistry, hematology, vital signs, and weight
- Columbia Suicide-Severity Rating Scale (C-SSRS)
- CYP2D6 genotyping
- 12-lead electrocardiograms (ECG)

Statistical methods:

If not otherwise specified, statistical significance is defined as $p \le 0.05$ and is two-tailed when appropriate. Data base lock will occur after 4-week ST double-blind period. The primary efficacy variable is the change from baseline in the YMRS total score.

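### The 3-day cut-off in the adverse-event tables has no exception for serious events, so late SAEs that did not cause discontinuation drop out of the by-arm SAE display and SAE counts can disagree between tables

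*Combined protocol and SAP*

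**What the plan says.** Section 11.4.1.1 (Adverse Events) proceeds in this order.

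- Collection: "Adverse events will be recorded throughout the study and at early discontinuation".
- Definition: "Treatment-emergent adverse events will be defined as those events, which are newly occurring or worsening from baseline". No end of the treatment-emergent window is given.
- Tables: TEAEs by arm, by primary system organ class and preferred term, followed by "Similar displays will be provided for SAE".
- Cut-off: "Any event starting more than 3 days after the final dose of study medication will be excluded from the above tables and only listed", with one exception, "unless the event caused discontinuation".
- A further paragraph, placed after the cut-off: "The proportions of patients experiencing SAEs and AEs resulting in discontinuation from the study will be summarized by treatment groups".

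Section 11.4 names SAE frequency as part of the primary safety assessment. Section 11.4.1.6 asks for numbers and percentages of patients by arm for completed suicide, non-fatal attempts and other suicidal events, and states no cut-off in days. On timing, the synopsis says "Data base lock will occur after 4-week ST double-blind period".

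**The concern.** A short on-treatment window is a common choice for ordinary adverse events, because it keeps off-drug events from diluting the comparison. SAEs are usually handled differently. They are few, and those starting soon after stopping are of interest in their own right. Here the same cut-off covers both, because the SAE displays are among the tables that precede the rule and seriousness is not a ground for exemption.

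Two things are at stake. First, the term-level SAE display, which shows the kind of serious event in each arm, can be incomplete for the period just after stopping. Second, the plan can produce two by-arm SAE counts that differ, with nothing in the text to say which is the intended one.

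**Working it through.** The plan states no figure on this point, so there is nothing to reproduce. The check is a reading of the text, followed by an illustration on assumed rates.

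**Step 1: follow one event through the text.** Take an SAE that starts 5 days after the last double-blind dose in a patient who does not enter the extension, and that did not cause discontinuation.

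| Place | Is the event counted? |
|---|---|
| TEAE definition (11.4.1.1) | Yes, if new or worse than baseline; no end date is given |
| SAE display by system organ class and preferred term (11.4.1.1) | No: it comes before the cut-off and is subject to it |
| By-arm SAE proportions (11.4.1.1, after the cut-off) | Not settled: they are not literally among the tables above the rule, and no window is stated |
| C-SSRS counts by arm (11.4.1.6), if the event is suicidal | Yes, on the text; no cut-off is stated |
| Listings | Yes |

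The same event is therefore absent from one by-arm table, present in another if it is suicidal, and undetermined in a third.

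**Step 2: how much the exception restores.** An event that begins after the final dose cannot be the reason that dosing stopped. At most it can cause withdrawal from the study. The exception therefore keeps some late SAEs in the tables, but probably not many. Whether a death counts as having caused discontinuation is arguable, and the text does not say.

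**Step 3: illustration of size.** Inputs: n = 200 per arm (Section 11.1). Assumed, because the document gives neither: SAE incidence p of 2% to 6%, and a share s of 10% to 50% of SAE patients whose event is late and did not cause discontinuation.

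Patients with an SAE per arm = n × p: 200 × 0.02 = 4, up to 200 × 0.06 = 12.

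Patients lost from the display per arm = n × p × s:

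- lowest: 200 × 0.02 × 0.10 = 0.4
- middle: 200 × 0.04 × 0.25 = 2
- highest: 200 × 0.06 × 0.50 = 6

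The proportion of the display that is lost equals s by construction. The result therefore restates the assumption and does not estimate it. With counts this small, one or two patients would still visibly change an SAE table.

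**The case against.** The case on the other side is substantial.

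- **Not every late SAE is lost.** A reader who stops at the words about listing might infer that any death or suicide attempt after day 3 disappears from the tables. The text does not support that. Events that caused discontinuation stay in, excluded events are still listed, and Section 11.4.1.6 already counts suicides and attempts by arm.
- **Overall SAE frequency may be intact.** The SAE proportions come after the rule. If they are meant to be uncut, the overall frequency named in Section 11.4 is preserved and only the breakdown by term loses events. Two tables with different windows are not in themselves an error, provided that each is labelled. This stands, but neither table is labelled, and the text does not say which window the proportions use.
- **Open-label events.** A reader might also infer that, because the final dose is undefined and adverse events are recorded throughout the study, events on open-label iloperidone in former placebo patients would be counted against placebo. The document does not support this. The synopsis separates the short-term phase from the optional extension, gives the extension its own long-term safety objective, and places database lock after the 4-week double-blind period. Section 11.2.5 also limits the noncompliance summary to the double-blind phase. The natural reading is the last double-blind dose, under which any overlap with open-label dosing is at most 3 days. What is left is a missing definition.
- **Deferral to the SAP.** Sections 11.2 and 11.4.1.1 leave detail to the SAP, which may define the windows. That could settle the undefined term. The cut-off on the SAE display is different: it is a stated rule, and it stands unless the SAP changes it.

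**Conclusion.** The point holds as a limited one. As written, Section 11.4.1.1 removes from the by-arm SAE display any SAE that starts more than 3 days after the final dose and did not cause discontinuation. The SAE proportions and the C-SSRS counts state no such cut, so counts of serious events can disagree between tables.

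The size cannot be computed: the document gives no SAE rate and no share of late events. The range of 0.4 to 6 patients per arm rests wholly on the assumed rates.

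It would go too far to say that the safety comparison is miscounted. Nothing shows that it would be, or in which direction. Both issues, the late SAEs and the undefined final dose, concern how the window closes; its start is anchored to baseline. This is a cheap improvement to the safety tables, and the undefined final dose is a clarification to make at the same time.

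**What to change.** Before unblinding, change the text or specify in the SAP:

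1. Apply the 3-day cut-off only to the tables of non-serious TEAEs.
2. Tabulate all SAEs and deaths by arm, by system organ class and preferred term, up to the last double-blind-phase contact or the first open-label dose, whichever comes first. Use two columns: on-treatment (with the 3-day window) and all events.
3. Use the same window for the by-arm SAE proportions, so that they agree with the all-event column.
4. State that the final dose means the last double-blind dose, and that open-label events are summarized separately.

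The cost is a few sentences and one extra column. Section 11.2 allows changes of method made before unblinding to be documented in the SAP without a protocol amendment. The downside is that the all-event column will include some off-drug events; the on-treatment column keeps the view that the plan now gives.

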11.4.1.2. Laboratory Data

Clinical Laboratory Data

The summary statistics of raw data (hematology and chemistry) and change from baseline values will be presented, as well as shift tables from baseline to post-baseline values using normal ranges. For urinalysis parameters, the number and percentage of patients falling under each category of the test will be presented.

Clinical laboratory data will be summarized for each treatment group by presenting the proportions of patients with clinically notable abnormalities (Appendix 17.2).

Clinically notable values will be identified according to the criteria identified in the FDA's "Supplementary Suggestions for Preparing an Integrated Summary of Safety Information in an Original NDA Submission and for Organizing Information in Periodic Safety Updates" (Revised 2-APR-87) provided by the FDA Division of Neuropharmacological Drug Products (DNDP). Differences in incidence rates between the treatment groups will be tested as described in the SAP.

11.4.1.3. Vital Signs

Data from vital signs and body measurements will be listed, clinically notable values (Appendix 17.3) will be flagged, and any other information collected will be listed. Data will also be summarized by treatment group using mean change from baseline and proportions of patients with values outside the normal range, and values that were clinically notable.

11.4.1.4. Electrocardiogram (ECG)

Results from the ECG will be listed for each patient. These data will also be summarized for each treatment group by presenting patients with newly occurring or worsening ECG abnormalities.

11.4.1.5. Extrapyramidal Symptoms (EPS)

The observed value and change from baseline in AIMS, BAS and SAS will be tabulated by treatment and analyzed by ANCOVA. In addition, categorical responses, such as "worsened",

"unchanged" and "improved" may be derived from the AIMS, BAS or SAS scores and be compared between the two treatments. Details of the analysis will be provided in the SAP.

11.4.1.6. Columbia-Suicide Severity Rating Scale (C-SSRS)

Results from the C-SSRS will be listed for each patient. These data will also be summarized by treatment group and for suicidal ideation events, suicidal behaviors and completed suicides. In particular, for each of the following suicide related events, the number and percent of patients with the event will be enumerated by treatment group: completed suicide, nonfatal suicide attempt, interrupted attempt, aborted attempt, preparatory acts or behavior, active suicidal ideation with specific plan and intent, active suicidal ideation with some intent to act without specific plan, active suicidal ideation with any methods (no plan) without intent to act, non-specific active suicidal thoughts, and wish to be dead. Details of the analysis will be provided in the SAP.

11.5. Subgroup Analysis

The subgroup analysis (such as, sex, age, baseline illness severity etc.) for efficacy variables and safety variables may be conducted as described in the SAP.

11.6. Deviations in Analysis from Statistical Plan and Other Issues

During the analysis and reporting process, any deviations from the statistical plan designed for this protocol will be described and justified in the final report.
